e. Medication maintenance and adherence monitoring (Days 18-40). Trained study personnel will evaluate heart rate, orthostatic blood pressure, pre-syncope and syncope signs and symptoms once per week following the Lofexidine titration. If bradycardia, orthostatic hypotension, or signs/symptoms of pre-syncope or syncope are identified at any point, the dose of Lofexidine will be lowered to the prior tolerated Lofexidine dose and the participant will remain at that dose for the duration of the study. Participants will record themselves taking their medications A survey link will be sent to the participant's cell phone via app alert two to three times daily, depending on where they are in the medication schedule. Video capture will occur through the CREMA app. The research coordinator will review the subjects' videos before each study visit. As discussed, we have used this

technology successfully for medication adherence monitoring. To encourage compliance, participants will receive \$10 for each day that they complete their medication adherence videos.

- **f. Intervention phase** (Study Days 18-40). During the 5-week medication phase, study participants will come in three times per week for UDSs. Blood pressure and pulse will be assessed at each visit. If the SBP < 90 mmHg and > 20% below screening value and/or DBP is < 50 mmHg and > 20% below screening value, or the individual is complaining of symptoms of hypotension, the medication dosage will be reduced. If these symptoms do not resolve, the individual will be removed from the study and followed until vital signs normalize. EKG's will be performed at Weeks 4 and 6 to monitor QT intervals. A contingency-management procedure will be implemented to facilitate study visit adherence. The payments will start at \$4 and increase by \$4 for each consecutive visit.

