- **f. Assessments.** Self-Report Measures. Mood Rating Scale: As described above and used with the CREMA sessions, to allow for cross-task comparisons. State-Trait Inventory (STAI): The STAI is a 20-item self-report scale (Spielberger, 1983) employing a Likert-scale format with four responses per item (1-4). Ten of the STAI items measure feelings of stress and anxiety, while the remaining ten items measure feelings of relaxation. The STAI has good psychometric properties. Opioid craving will also be measured using a Likert scale format. We have had good success with this in prior studies in OUDs (Back et al., 2014) Physiological Measures. Heart rate and blood pressure will be measured using an intermittently inflatable cuff as indices of physiological arousal during the test session. Hormonal Measures. Cortisol: Cortisol will be measured in unstimulated passive saliva using the Salimetrics expanded range, high sensitivity salivary cortisol enzyme immunoassay kit. This kit has a lower sensitivity level of <0.003 μg/dL. The correlation between salivary and serum cortisol has been shown to be high (r=0.91, p<0.0001). Cortisol is commonly measured as an indication of stress response in human laboratory studies.

Modifications may be made to lab day procedures if necessary for patient and staff safety, ie fewer confederates, remote procedures.

- **g. Discharge.** Following assessments, participants will be given instructions to taper their lofexidine over the next five days. A member of the research staff will be available to discuss management of any craving or urges to use any substance if craving remains elevated at the end of study procedures.
- **C.2.c.6. Follow-up Assessment (Days 41-47).** During a one-week follow-up period, lofexidine will be tapered... They will come to the two times during the taper for BP monitoring (0.72 BID for two days, 0.36 mg BID for 2 days, 0.36 QD for 1 day). After five days, participants will return to the clinic and return clinic-provided phones, complete a questionnaire regarding their experience with the CREMA and REDCap surveys, and be provided referrals to treatment if interested.

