#### c. Potential Risks

1. Risks due to lofexidine: A Cochrane review provides a comprehensive overview of adverse events associated with lofexidine and other alpha-adrenergic agents (Gowing et al., 2009). Adverse events associated with lofexidine are primarily related to its alpha-adrenergic agonist effects. Hypotension has been reported (Yu et al., 2008; Gowing et al., 2009; Khan et al., 1997), but generally this was mild and studies comparing lofexidine with other alpha-agonists found that hypotension was seen less frequently with lofexidine. Rebound increase in blood pressure after lofexidine discontinuation has also been reported (Yu et al., 2008), but was not severe enough to require intervention. Sedation, dizziness and dry mouth have also been reported with lofexidine at higher rates than placebo, but lower when compared to other alpha-agonists (Khan et al., 1997; Gowing et al., 2009). A case report (Schmitter et al., 2004) and a dose escalation study (Schmitter et al., 2009) report QTc interval prolongation in individuals with lofexidine added to methadone, but there have been no reports of QTc prolongation with lofexidine monotherapy.

- 2. Risks due to study procedures: Participants will be asked not to use illicit opioids for 7 days, however all will be stabilized on buprenorphine or methadone so there should be no risk of opioid withdrawal symptoms.
- 3. Potential risks of rating scales and questionnaires: These are all non-invasive, should add no risk, and have been used without difficulty or any adverse events in our previous studies. The only minor inconvenience could be the time taken to complete them. Some participants may feel uncomfortable disclosing personal thoughts and feelings.
- 4. Risks of stress induction procedures: There is a small risk of increased stress or opioid craving as a result of the CREMA procedures; however, it will likely not differ substantially from the reactivity elicited by stimuli commonly encountered in the day-to-day environment of study participants. Participants that report sustained significant stress or craving after the laboratory session will be provided a debriefing to address symptoms.

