#### b. Protections Against Risks

All study participants will be closely monitored for psychiatric and medical stability. All sessions will be conducted under the supervision of experienced personnel. If crisis intervention is necessary, senior staff will be available to evaluate the subject and provide an intervention or referral. If hospitalization is indicated, the patient will be hospitalized through the Center for Drug and Alcohol Programs at MUSC or an appropriate referral will be made. All participants will be fully informed that they may withdraw from the study at any time without penalty.

Lofexidine will be titrated over ten days when it is initiated. Participants will be seen by a medical provider on three times a week uring dosage escalation and orthostatic hypotension testing will be done. The medical provider will inform the participant, verbally and with a hand-out to take home, concerning common side effects of lofexidine (dizziness, somnolence, dry mouth) and precautions to minimize risks associated with blood pressure decreases (hydration, standing up slowly). The target dose of lofexidine is 2.16 mg per day, but if hypotension or other troublesome side effects develop, the medical provider may slow the titration for that individual. At the end of the study, medications will be tapered over a five-day period. Participants will be seen every other day during medication taper and blood pressure will be monitored.

To ensure confidentiality, all participant data will be coded by letters and/or numbers, and only the investigators will have access to the master lists of codes. All participant records will be kept in a locked cabinet in an office that will be locked at times when not in use. Participants who screen remotely and have virtual medication monitoring visits will be instructed to find a private location to conduc these visits. The research staff understands the importance of maintaining confidentiality, and this method of maintaining confidentiality has been used for several years by our research group and has been effective. All electronic databases are stored on HIPAA-compliant servers with restricted access. All co-investigators and study personnel have completed (or will complete upon hiring) training in Good Clinical Practices as mandated by NIH and the MUSC IRB.

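### Rebound blood pressure after stopping lofexidine is a named risk, yet no blood pressure is scheduled after the last taper dose or described for most early leavers

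*Combined protocol and SAP*

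**What the plan says.** Under Potential Risks, item 1, the protocol states: "Rebound increase in blood pressure after lofexidine discontinuation has also been reported". The same sentence qualifies this: "but was not severe enough to require intervention".

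Section C.2.c.6 (Follow-up Assessment, Days 41-47) gives the taper as "0.72 BID for two days, 0.36 mg BID for 2 days, 0.36 QD for 1 day" and says of monitoring: "They will come to the two times during the taper for BP monitoring". Of the visit once the five days are over it says: "participants will return to the clinic and return clinic-provided phones, complete a questionnaire regarding their experience with the CREMA and REDCap surveys". Referrals to treatment are also offered there. No BP or pulse is listed for that visit.

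Protections Against Risks (section 2.b) confirms the length, "At the end of the study, medications will be tapered over a five-day period", but words the checks differently: "Participants will be seen every other day during medication taper and blood pressure will be monitored".

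For people who leave during treatment, C.2.c.5 item f covers one group. If low BP or its symptoms persist after dose reduction, "the individual will be removed from the study and followed until vital signs normalize". No taper, BP check or safety visit is described for those who leave for other reasons.

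**The concern.** The protocol ties this risk to discontinuation, but its scheduled measurements end while the drug is still being taken. The one clinic visit after the last dose lists only administrative and questionnaire content. A participant who stops unplanned may have no further BP reading at all.

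At stake is safety information, not an efficacy result. Adverse events are identified from self-report and from what is done at visits (Regulatory Issues). A rise without symptoms is therefore found only if someone measures BP. The monitoring board is charged with the rate and severity of adverse events, and on this risk it would have no scheduled off-drug readings.

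**Working it through.** The point rests on the schedule, so the check is a timeline and a head count. No power or error-rate formula applies.

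1. **Taper length.** The steps in C.2.c.6 are 2 + 2 + 1 = 5 days. This reproduces the five days stated in section 2.b.

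2. **Position in the study.** With the second laboratory session on day 40 and the taper starting on day 41, the taper covers days 41 to 40 + 5 = 45. The return visit then falls at about day 46, inside the day 41-47 window and after the last dose. Laboratory sessions may be rescheduled by up to a week. That moves the dates but not the order.

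3. **Doses at the taper checks.** Full dose is 3 x 0.72 = 2.16 mg/day. The taper gives 2 x 0.72 = 1.44, then 2 x 0.36 = 0.72, then 0.36 mg/day. By the last step the dose has fallen by (2.16 - 0.36)/2.16 = 83%. Taper checks therefore take place during a real reduction, but none is placed after the last dose.

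4. **Number of taper checks.** C.2.c.6 says two. Every other day over days 41-45 gives three (41, 43, 45) or two (42, 44), so the sections agree only on the second pattern. The payments do not settle it. The listed fixed amounts are 40 + 20 + 20 + 25 + 30 + 364 + 100 + 50 + 100 = $749. Adding $10 per check gives $769 for two or $779 for three, against a stated $819.

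5. **Readings after the last dose.** The number listed is 0. The rule in C.2.c.5 item f that BP and pulse are taken at each visit belongs to the intervention phase (days 18-40). Payment for BP checks is likewise tied to the tapering phase.

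6. **Early leavers.** The power section gives 25% attrition and 136 randomized, 68 per arm. Expected leavers are 0.25 x 136 = 34. Per arm this is 0.25 x 68 = 17 if losses are equal, which is an assumption. Expected completers are 136 - 34 = 102.

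7. **Action rules.** The rules in C.2.c.5 items d to f respond to low BP, orthostatic drops, bradycardia, and pre-syncope or syncope. None mentions a raised value.

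**The case against.** Several points on the other side have force.

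- **Severity.** The protocol's only statement on how serious rebound was is that no intervention was needed. This stands and limits the weight of the point.
- **The taper checks are informative.** They occur while the dose falls by up to 83%, so a rise on dose reduction could be seen there. The documents give no half-life, clearance time or time of rebound onset. A reader might infer that rebound cannot be detected at all, or that the trial is bound to report none. The documents do not support that.
- **Some leavers are followed.** A reader might infer that nobody who leaves early has BP checked. That is wrong for those removed for unresolved hypotension, although that follow-up begins from low BP and is not described as a rebound check.
- **General safety reporting exists.** Adverse events are monitored throughout, a study physician evaluates them, and a board reviews rate and severity. A detailed monitoring plan is also promised and is not in the file. Symptomatic rebound in people still in contact thus has a route to detection. A symptomless rise does not. Event follow-up may also end once a participant is out of the study.
- **The 34 is not a count of abrupt stops at full dose.** It is all-cause attrition across both arms. It includes people who leave during titration, people held at a lowered dose, and people removed for hypotension who are followed. It is only an upper-level guide.
- **Leavers may be unreachable.** They may withdraw at any time, so data from them will be incomplete.

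None of this explains why the visit that already takes place off drug omits BP.

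**Conclusion.** The point holds in a limited form. No BP is scheduled after the last taper dose although a clinic visit takes place then, and none is described for early leavers other than those removed for unresolved hypotension. A symptomless rise after the last dose or an unplanned stop could be missed.

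The size is 0 scheduled off-drug readings for about 102 expected completers, and no described check for most of about 34 early leavers. About 17 of those leavers would be on lofexidine, at varying doses. These figures assume that the taper starts on day 41, that attrition is the planned 25%, and that losses are equal between arms.

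This is an inexpensive gap in safety measurement. The documents do not show that participants are left unprotected from a serious hazard. Separately, C.2.c.6 and section 2.b should state the same number of taper checks.

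**What to change.** - Add BP and pulse to the listed assessments at the post-taper visit in C.2.c.6. This would give up to about 102 off-drug readings with a randomized, blinded placebo comparison.
- Record BP and pulse at any final contact with early leavers who can be reached. The home cuffs described under virtual monitoring could make this feasible for those who hold one.
- Reconcile C.2.c.6 (two taper checks) with section 2.b (every other day, so two or three in five days).
- Reconcile the discontinuation risk under Potential Risks with BP action rules that cover only low values. How a raised value is managed is for the sponsor's medical team to decide.

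The cost is a few minutes at a visit already scheduled and paid at $100, some effort to contact leavers, and an amendment. Data from leavers will be incomplete and should be reported as such.

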- d. Lofexidine/Placebo Titration Procedures (Days 8-17). After two consecutive negative drugs screens have been obtained, participants will be randomly assigned to study medication (lofexidine or matching placebo). For the Shoreline site, medication will be dispensed by IDS and delivered to MUSC staff at that site. At the randomization visit, females will provide saliva samples for estradiol and progesterone testing. Trained study personnel will evaluate heart rate, orthostatic blood pressure, and pre-syncope and syncope signs and symptoms prior to the initiation of Lofexidine. Lofexidine will not be dispensed if the participant is found to have

one of the following on physical exam: 1) clinically significant bradycardia as determined by study physician; 2) orthostatic hypotension defined as a systolic blood pressure decrease of at least 20mm Hg or a diastolic blood pressure decrease of at least 10mm Hg within three minutes of standing; 3) participant endorsement of presyncope symptoms such as lightheadedness, muscular weakness, blurred vision, or feeling faint during the evaluation of orthostatic blood pressure; or 4) syncope (fainting) during the evaluation of orthostatic blood pressure. Participants with bradycardia, orthostatic hypotension, pre-syncope or syncope would be terminated from the study and study staff will facilitate appropriate follow-up medical care. To minimize risks of hypotension, lofexidine will be titrated over a 10-day period with 0.36 mg QDfor days 1 and 2; 0.36 mg BID for days 3 and 4; 0.36 mg TID for days 5 and 6; 0.36 mg BID and 0.72 QD days 7 and 8; 0.37 QD and 0.72 BID for days 9 and 10, and 0.72 mg TID on day 11 and throughout the rest of the study (see **Table 2**). This is the dose recommended by the regulatory agencies in England and the titration schedule is consistent with lofexidine titration in 8 published studies (Gish et al., 2010).

Table 2

| Days                                      | AM Dose (mg) | PM Dose (mg) | QHS Dose (mg |
|---|--------------|--------------|--------------|
| Days 1 and 2 (Study days 8 and 9)         |              |              | 0.36         |
| Days 3 and 4
(Study days 10 and
11) | 0.36         |              | 0.36         |
| Days 5 and 6 (Study days 12 and 13)       | 0.36         | 0.36         | 0.36         |
| Days 7 and 8 (Study days 14 and 15)       | 0.36         | 0.36         | 0.72         |

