| Days 9 and 10 (Study days 16 and 17)      | 0.36         | 0.72         | 0.72         |
| Days 11-40
(Study days 18-40)          | 0.72         | 0.72         | 0.72         |

Trained study personnel will evaluate heart rate, orthostatic blood pressure, pre-syncope and syncope signs and symptoms at all study visits during the titration period. If the study participant does not have bradycardia, orthostatic hypotension, or pre-syncope or syncope signs or symptoms as defined above, the dose of Lofexidine will be increased according to the titration schedule (**Table 2**). If bradycardia, orthostatic hypotension, or signs/symptoms of pre-syncope or syncope are identified at any point, the dose of Lofexidine will be lowered to the prior tolerated Lofexidine dose and the participant will remain at that dose for the duration of the study. At the beginning of the study, participants will be given a rescue pack of 36 tablets in case visits are missed. This will cover 3 days at the full dose.

The medical provider will inform the participant, verbally and with a take-home hand-out, of common side effects of lofexidine (dizziness, somnolence, dry mouth) and precautions to minimize risks associated with blood pressure (BP) decreases (hydration, standing up slowly). Participants will attend study visits three times a week during the induction period and throughout the study during which a UDS will be collected. The MUSC Investigational Drug Service will be responsible for randomization, will keep a record of the blind and will be available should unblinding be required. In the event that WorldMeds is unable to supply matching placebo. lofexidine tablets (supplied by US WorldMeds) will be encapsulated along with matching placebo capsules by Pitt Street Pharmacy, a specialty compounding pharmacy. Randomization will be stratified on presence/absence of other substance use as well as the presence/absence of significant childhood trauma (ACE>4).

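### The only printed lofexidine taper starts at 1.44 mg/day and has no version for participants held at 1.08 mg/day or less; a one-line ceiling should be added

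*Combined protocol and SAP*

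**What the plan says.** **The taper.** Section C.2.c.6 (Follow-up Assessment, Days 41-47) prints one schedule: "0.72 BID for two days, 0.36 mg BID for 2 days, 0.36 QD for 1 day". The other statements about stopping treatment add no doses. Item g (Discharge) of Phase Two says "participants will be given instructions to taper their lofexidine over the next five days", and section 2.b (Protections Against Risks) gives a five-day length.

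**The hold.** Section C.2.c.5 item d covers titration and item e covers maintenance. Each provides that, after bradycardia, orthostatic hypotension, pre-syncope or syncope, "the dose of Lofexidine will be lowered to the prior tolerated Lofexidine dose". Both items then fix the reduced dose, stating that "the participant will remain at that dose for the duration of the study".

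**Other dosing rules.** Item f (Intervention phase) reduces the dose for low blood pressure or hypotensive symptoms, without saying by how much, and removes the participant if the problem persists. Section 2.b adds that, for troublesome side effects, "the medical provider may slow the titration for that individual".

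**Monitoring in the taper.** Section C.2.c.6 has two blood-pressure visits. Section 2.b says "Participants will be seen every other day during medication taper and blood pressure will be monitored".

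**The concern.** Table 2 has steps below 1.44 mg/day, and the hold rule can leave a participant on one of them until day 40. For that participant the first line of the printed taper is an increase.

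The people concerned have already had a haemodynamic sign or symptom on study medication. The protocol itself treats the speed of dose increase as a safety matter: "To minimize risks of hypotension, lofexidine will be titrated over a 10-day period". For an event at 0.72 or 1.08 mg/day, the literal taper would start above the dose at which the event occurred. For an event at 1.44 mg/day it would start at that dose. Blood-pressure checks during the taper may detect a fall, but they come after the dose has been raised.

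**Working it through.** **Inputs.** The titration steps come from section C.2.c.5 item d and Table 2, the target dose from section 2.b, and the taper from section C.2.c.6.

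**Reproducing the plan's figure.** Full dose: 3 × 0.72 = 2.16 mg/day, which matches the stated target.

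**Daily totals during titration.**
- Study days 8-9: 0.36 mg
- Days 10-11: 2 × 0.36 = 0.72 mg
- Days 12-13: 3 × 0.36 = 1.08 mg
- Days 14-15: 0.36 + 0.36 + 0.72 = 1.44 mg
- Days 16-17: 0.36 + 0.72 + 0.72 = 1.80 mg
- From day 18: 2.16 mg

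**Daily totals during the taper.** 2 × 0.72 = 1.44 mg on two days, 2 × 0.36 = 0.72 mg on two days, then 0.36 mg on one day. The sum is 2.88 + 1.44 + 0.36 = 4.68 mg.

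**Comparison.** The held dose is one step below the event dose. Ratio to held dose = 1.44 / held; ratio to event dose = 1.44 / event. A capped taper takes, on each day, the smaller of the printed dose and the held dose. Excess = 4.68 minus the capped total.

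| Event dose (mg/day) | Held dose (mg/day) | Start ÷ held | Start ÷ event | Taper days above held | Capped total (mg) | Excess (mg) |
|---|---|---|---|---|---|---|
| 0.72 | 0.36 | 4.0 | 2.0 | 4 | 1.80 | 2.88 |
| 1.08 | 0.72 | 2.0 | 1.33 | 2 | 3.24 | 1.44 |
| 1.44 | 1.08 | 1.33 | 1.0 | 2 | 3.96 | 0.72 |
| 1.80 | 1.44 | 1.0 | 0.8 | 0 | 4.68 | 0 |
| 2.16 | 1.80 | 0.8 | 0.67 | 0 | 4.68 | 0 |

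**Largest single dose.** Participants held at 0.36, 0.72 or 1.08 mg/day take no single dose above 0.36 mg, so the 0.72 mg taper dose is twice that. Participants held at 1.44 or 1.80 mg/day already take a 0.72 mg dose, so their largest single dose does not rise.

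**How a participant gets there.** One step-down leads to an affected held dose only if the event occurs at 0.72, 1.08 or 1.44 mg/day. Those doses are scheduled on study days 10-15, which is 6 of the 33 planned dosing days (8 to 40). From 2.16 mg/day, three step-downs are needed to reach 1.08 (2.16, 1.80, 1.44, 1.08). The 6 of 33 describes the schedule. It is not a probability, and the documents give no event frequency.

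**The case against.** The strongest objection is that nobody would read the taper this way. The hold lasts for the duration of the study, days 41-47 are part of the study, and going from 0.36 to 1.44 mg/day is not a taper. On this view the parenthesis is simply the descent from 2.16 mg/day, and the hold already acts as a ceiling. Most of this stands, and it is the more natural intent. A reader might infer that the protocol means to re-escalate participants who could not tolerate the drug; the documents do not support that. What remains is that the only printed numbers contradict the hold for three of the six dose steps, and nothing says which prevails.

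The sentence carrying the taper is also visibly broken, and the discharge instructions given to participants are not in the documents. The finding is therefore limited to the text available.

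Other protections exist. Item f shows that the protocol's response to hypotension is to reduce the dose or remove the participant, which also makes three successive step-downs from the full dose less plausible. But it is written for the medication phase. Slowing the titration concerns the way up. Neither tells staff how to taper a participant on a held dose.

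Finally, rebound is a weak reason to insist on five days. Section 1.c notes that "Rebound increase in blood pressure after lofexidine discontinuation has also been reported", but adds that it did not need intervention. That is accepted: a shorter taper for low held doses is also reasonable.

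**Conclusion.** The point holds as a minor participant-safety correction. One taper is printed, and it fits the target dose. Applied literally, it would put participants held at 0.36, 0.72 or 1.08 mg/day on 1.44 mg/day for taper days 1-2, a rise of 1.08, 0.72 or 0.36 mg/day. That contradicts the rule that they stay at the tolerated dose.

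This rests on two conditions: that a participant reaches day 40 on one of those doses, and that staff follow the printed numbers rather than the hold. The number affected is unknown and probably small. Only active-arm participants would receive more drug.

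A reader might go further and infer a serious safety defect or a threat to the results. Neither is supported. The documents give no event rate, the likely intent is a ceiling, and blood pressure is monitored during the taper. The taper begins after the day 39-40 laboratory sessions and the treatment period used for the daily-life and relapse analyses, so the randomised comparison is not affected.

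**What to change.** Add to section C.2.c.6, identically in both arms so that the blind is kept:

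*The total daily dose and the largest single dose during the taper may not exceed those the participant was taking at day 40. Participants on less than 1.44 mg/day remain at their held dose until the printed schedule falls below it (or join the printed schedule at the first step not above their held dose).*

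The sponsor should choose one of the two options:

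| Held dose (mg/day) | Option 1: remain at held dose, five days | Option 2: join the schedule |
|---|---|---|
| 1.08 | 0.36 mg TID 2 days, BID 2 days, QD 1 day | 0.36 mg BID 2 days, QD 1 day |
| 0.72 | 0.36 mg BID 4 days, QD 1 day | 0.36 mg BID 2 days, QD 1 day |
| 0.36 | 0.36 mg QD 5 days | 0.36 mg QD 1 day |

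Participants on 1.44, 1.80 or 2.16 mg/day follow the schedule as printed. Referring to the largest single dose avoids ambiguity for those on 1.44 mg/day (0.36, 0.36 and 0.72 mg).

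Option 1 keeps the five-day length and the visit plan, but leaves a participant held at 0.36 mg/day on drug for five days with no step down before stopping. Option 2 is simpler and shorter. Either removes the rise.

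The cost is taper handouts and dispensing instructions by held dose: four versions under option 1 (the printed schedule plus three) and three under option 2, where the 1.08 and 0.72 mg/day schedules coincide. No extra visits are needed.

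### The protocol's only taper starts at 1.44 mg/day, which is above the daily dose of any participant held at 0.36, 0.72 or 1.08 mg/day after a haemodynamic reaction

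*Combined protocol and SAP*

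**What the plan says.** Titration (C.2.c.5 Phase 1, item d and Table 2) raises the dose in six steps, from 0.36 mg once daily to 0.72 mg three times daily. The first three steps are "0.36 mg QDfor days 1 and 2; 0.36 mg BID for days 3 and 4; 0.36 mg TID for days 5 and 6". The trigger for a reduction is broad: "If bradycardia, orthostatic hypotension, or signs/symptoms of pre-syncope or syncope are identified at any point". The consequence is that the dose is "lowered to the prior tolerated Lofexidine dose and the participant will remain at that dose for the duration of the study". Item e repeats this rule for the maintenance period, again stating that "the participant will remain at that dose for the duration of the study".

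For the end of treatment, the discharge paragraph of Phase Two says that "participants will be given instructions to taper their lofexidine over the next five days". C.2.c.6, Follow-up Assessment (Days 41-47), supplies the schedule: "0.72 BID for two days, 0.36 mg BID for 2 days, 0.36 QD for 1 day". Protections Against Risks (2.b) says only that "At the end of the study, medications will be tapered over a five-day period". None of these places ties the schedule to the dose the participant is taking when it begins.

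The two accounts of taper visits also differ. C.2.c.6 has two visits for blood pressure, whereas 2.b has participants seen every other day.

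**The concern.** A taper is meant to bring the dose down. A single fixed schedule does so only for participants who enter it above its first stage. The hold rule creates participants who may be below that stage, and they are there because they showed a cardiovascular reaction or related symptoms at a higher dose. If discharge staff hand out the printed schedule as it stands, some of these participants would be told to take more than the dose at which they had been held. Study medication is blinded, so the same sheet could reach participants in either arm, but extra active drug would be taken only in the lofexidine arm.

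What is at stake is participant safety. The laboratory sessions are on days 39 and 40 with participants still on study medication, the ambulatory analysis uses the five-week medication period, and time to relapse is cut off at day 40. The taper comes after these.

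**Working it through.** **Inputs.** Table 2 gives the doses at each step. The item d text prints 0.37 where Table 2 has 0.36 for days 9 and 10; Table 2 is used here. C.2.c.6 gives the taper.

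**Reproducing the plan's own figures.** Full dose: 3 x 0.72 = 2.16 mg/day, which matches the target stated in 2.b. Taper length: 2 + 2 + 1 = 5 days, which matches the five days stated in the discharge paragraph and in 2.b.

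**Taper stages.** Days 1-2: 2 x 0.72 = 1.44 mg/day. Days 3-4: 2 x 0.36 = 0.72 mg/day. Day 5: 0.36 mg/day.

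**Comparison with each step.** Change = taper stage minus held daily total; ratio = 1.44 / held daily total.

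| Step and doses (mg) | Daily total (mg) | Change, taper days 1-2 (mg) | Ratio | Change, taper days 3-4 (mg) |
|---|---|---|---|---|
| 1: 0.36 | 0.36 | +1.08 | 4.00 | +0.36 |
| 2: 0.36 + 0.36 | 0.72 | +0.72 | 2.00 | 0 |
| 3: 0.36 + 0.36 + 0.36 | 1.08 | +0.36 | 1.33 | -0.36 |
| 4: 0.36 + 0.36 + 0.72 | 1.44 | 0 | 1.00 | -0.72 |
| 5: 0.36 + 0.72 + 0.72 | 1.80 | -0.36 | 0.80 | -1.08 |
| 6 (target): 0.72 + 0.72 + 0.72 | 2.16 | -0.72 | 0.67 | -1.44 |

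Step 6 is the target and not a step to which anyone is reduced, so there are five possible held steps. The daily total rises at three of them. At those three steps the largest single dose also doubles, from 0.36 to 0.72 mg. At step 4 the daily total is the same, but it is taken as two doses of 0.72 mg instead of one of 0.72 mg and two of 0.36 mg.

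**Comparison with the dose that triggered the reduction.** Assume one step back, so that the reaction occurred at the next row of Table 2.

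- Held at 0.36 mg/day, reacted at 0.72: 1.44 / 0.72 = 2.0 times the triggering daily dose.
- Held at 0.72 mg/day, reacted at 1.08: 1.44 / 1.08 = 1.33 times.
- Held at 1.08 mg/day, reacted at 1.44: 1.44 / 1.44 = 1.0, the same daily total in fewer, larger doses.

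In all three cases the first taper stage returns the participant to at least the daily dose at which the reaction occurred.

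**The case against.** The strongest reply is that the two rules need not collide. Item d uses similar language for the full dose, which is to continue through the rest of the study, yet Table 2 ends that dose at study day 40 and C.2.c.6 then tapers it. On that reading the hold also ends at day 40. Read with complete literalness, the hold would forbid even a downward taper. The schedule could also be meant for full-dose participants only: it stands in parentheses in a garbled sentence, and an increase is not a taper in the ordinary sense. This stands far enough that a reader should not infer that the two rules cannot both be followed. It does not remove the gap. The schedule is printed without any such limit, and the only individual discretion that 2.b states is to slow the titration.

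A reader might also infer that every participant who was cut back would receive an increase. Table 2 does not support this. A first step back from full dose lands at 1.80 mg/day, and from there the taper lowers the dose. Increases arise mainly for participants stopped early in titration, or possibly after the separate blood-pressure reduction in item f, whose size is not stated.

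A third tempting inference is that safety checks fall away during the taper. The documents do not show this. Two checks in five days is 2 / 5 x 7 = 2.8 per week, against three visits per week during treatment, and 2.b has participants seen every other day. What can be said is narrower: orthostatic testing and heart rate are not named for the taper, and the two descriptions of visit frequency need aligning.

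Finally, the documents do not show that adverse events would follow. The risk section describes reported hypotension as generally mild. An increase in dose could cause events; that it would is not established.

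**Conclusion.** The point holds in a limited form. Applied as printed, the single taper starts above the held daily dose for participants held at 0.36, 0.72 or 1.08 mg/day (4.0, 2.0 and 1.33 times), and at 0.36 mg/day its second stage is above it too. It leaves the total unchanged at 1.44 mg/day and lowers it at 1.80 mg/day. Three of five is a count of possible steps, not a share of participants: the documents give no expected number held at each step, so the number affected cannot be computed.

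The conclusion rests on two assumptions: that the held dose is a row of Table 2, and that the schedule in C.2.c.6 is given to all participants, as the absence of any variant implies. It bears on participant safety and not on the efficacy comparisons. It is still worth correcting before anyone is discharged on this schedule, because the printed instruction would raise the dose in people held back for a haemodynamic reaction.

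**What to change.** The sponsor's medical team should reconcile C.2.c.6 and Protections Against Risks (2.b) with items d and e of C.2.c.5. The revised text should state how the end-of-treatment schedule applies to participants held below the target dose and whether the hold rule extends beyond day 40. It should also give a single description of taper visits. The discharge instructions should then be aligned with that text in a way that keeps the blind. No dose or taper rule is proposed here; the content is for the medical team.

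The cost is a short protocol amendment and revised pharmacy and discharge sheets. Reconciling the dosing text needs no additional participants or visits; aligning the visit descriptions means choosing between two visits and every other day, which over five days differ by at most one visit.
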